Hamlet TRIAL

PROTOCOL

Full title: Multicenter randomized controlled trial of Doppler guided Hemorrhoid Artery Ligation (DGHAL) and mucopexy versus mucopexy alone in the treatment of grade III Hemorrhoids.

S

hort title: Hamlet (Hemorrhoids Artery Mucosal Ligation prospEctive Trial) trial.

Alternative title: Doppler-guided or non doppler-guided arterial ligation and mucopexy for third degree hemorrhoids? That is the question. The Hamlet (Hemorrhoids Artery Mucosal Ligation prospEctive Trial) trial.

Developed by Department of Emergency and Organ Transplantation (DETO), University of Bari,
Italy

Hamlet Trial Management Group

Surgery

[name], MD, [name]

Dept of Emergency and Organ Transplantation, University of Bari, Italy,
c/o Azienda Ospedaliero-Universitaria Policlinico di Bari, [name]
[contact] Mobile [contact]

[contact]

e-mail: [contact]

Randomization

Simple randomization will be centralized and carried out by assigning the 3 treatment options to consecutive computer generated random number obtained through the website http://www.randomizer.at

The randomization code will be obtained by contacting the number or the [contact]/ [name] or by the e-mail address [contact] or [contact].

Clinical queries during office hours should be directed to one of the clinical coordinators or to an appropriate member of the Hamlet Management Group

Data Monitoring and Ethics Committee

Clinical data monitoring will be carried out by [name]: Dept of Emergency and Organ transplantation, University of Bari e-mail: [contact] [contact]

Independent Ethics Committee of the Azienda Ospedaliero Universitaria Policlinico Consorziale Bari

[name]

[contact] [contact] e-mail: [contact]

Protocol approval n. 4555/2014

Trial Sponsor: University of Bari, Department of Emergency and Organ Transplantation, DETO,

Section of Surgery, Bari, Italy, [contact] - [name]

Clinicaltrial.gov ID number: Protocol version: 14/3/18

Hamlet Study Office

For general queries, supply of trial materials, and collection of data:

Trial Coordinator: [name], mobile [contact] – office [name] e-mail [contact]

Computing: [name], MD – mobile [contact] – e-mail: [contact]

CONTENTS

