2. STUDY HYPOTHESIS

The hypothesis of the study is that a simple mucopexy procedure by suture-fixation of anal cushion without the aim of a Doppler device, could be as effective as DGHAL and mucopexy to manage prolapsing grade III hemorrhoids.

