3. STUDY DESIGN

3.1 General Design

Prospective, multi-centre, parallel-arm randomized controlled equivalence trial. Eligible patients will be randomized to either mucopexy without Doppler guided artery ligation or mucopexy with doppler guided hemorroidal artery ligation.

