3.2.1 Primary

[figure not shown]
Primary aim of the Hamlet trial is to demonstrate that mucopexy without DGHAL for grade III haemorrhoids have equivalent recurrence rate at 1 year follow up of DGHAL with mucopexy procedure

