4.2 Operative protocol

Patients with symptomatic grade III haemorrhoids will enter the study if they fulfil the entry and exclusion criteria and after written informed consent. They will be randomized in 2 groups: DGHAL with mucopexy (group A) and DGHAL without mucopexy (group B).

A cleansing enemas will be performed early in the morning at least 2 h before the operation. Antibiotic prophylaxis was not considered.

General or epidural anaesthesia will be performed according to the patient or anaesthetist preferences.

A urinary catheter will be inserted in all patients and removed after few hours from the operation.

The patients will be placed in the lithotomy position.

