5. STATISTICAL ANALYSIS

5.1 Sample Size Determination:

A sample size calculation shows that 100 subjects per arm will suffice for accepting of the equivalent hypothesis with power of 0.8 and a type I error probability of 0.05, an equivalent limit of 15% and expected percentage of success in both control and experimental group of 90% (sample size calculated with R).

5.2 Statistical Methods:

Results will be expressed as either mean and standard deviation (SD) or frequency (percentage). Between-group comparisons will be performed using Student's t-test (normally distributed data) or Mann-WhitneyU test (skew data) for continuous variables or Chi-square test for categorical variables. All hypotheses will two-tails with p < 0.05 considered as statistically significant.

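### The randomisation instruction assigns three unnamed options in a two-arm trial, and Section 4.2 defines group B as something other than the mucopexy-alone comparator

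*Protocol*

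**What the plan says.** **Number of options.** The Randomization paragraph in the front matter states: "Simple randomization will be centralized and carried out by assigning the 3 treatment options to consecutive computer generated random number". The three are not named there or anywhere else. Other sections describe two arms:

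- Section 3.1: "Eligible patients will be randomized to either mucopexy without Doppler guided artery ligation or mucopexy with doppler guided hemorroidal artery ligation".
- Section 3.4 refers to both treatments when it describes what patients are told.
- Section 4.2 speaks of two groups.
- Section 5.1 says that "100 subjects per arm will suffice" and assumes an "expected percentage of success in both control and experimental group of 90" percent.
- Section 6.1 refers to both study arms.

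Section 3.3 also describes the allocation sequence but gives no number of arms, so it does not settle the matter.

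**Definition of group B.** Section 4.2 states: "They will be randomized in 2 groups: DGHAL with mucopexy (group A) and DGHAL without mucopexy (group B"). Elsewhere the comparison is different. The title has "Doppler guided Hemorrhoid Artery Ligation (DGHAL) and mucopexy versus mucopexy alone". Section 2 describes the tested procedure as "a simple mucopexy procedure by suture-fixation of anal cushion without the aim of a Doppler device". The primary aim in Section 3.2.1 is to show that "mucopexy without DGHAL for grade III haemorrhoids have equivalent recurrence rate at 1 year follow up of DGHAL with mucopexy procedure". Section 4.2.1.3 gives the non-Doppler group a mucopexy at fixed clock positions.

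**Devices.** Section 3.2.2 lists a comparison of the THD and AMI devices as a secondary endpoint. Section 4.2.1.2 allows either device and gives no rule for assigning one.

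**The concern.** These are not background statements. The front-matter paragraph is the text that tells whoever sets up the list how treatments are attached to random numbers, and Section 4.2 defines the arms for the operating teams. Followed as written, the first yields a list with three options in a trial designed, sized and explained to patients as having two. The second yields a comparator that does not match the primary aim.

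The status of one secondary endpoint also depends on which text is followed. If the device were one of the randomised options, the THD-versus-AMI comparison would be randomised. Under the two-arm text, nothing in the protocol makes it so.

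**Working it through.** **1. The plan's own sample size.** Inputs from Section 5.1: success 90% in both groups, equivalence limit 15 points, power 0.8, type I error 0.05, 100 per arm. For two one-sided tests with beta split over both sides:

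n per arm = 2 × 0.9 × 0.1 × (z(1−a) + z(0.90))² / 0.15²

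- a = 0.05 per side: 8 × (1.645 + 1.282)² = 68.5, so 69; with continuity correction 82.
- a = 0.025 per side: 8 × (1.960 + 1.282)² = 84.1, so 85; with continuity correction 97.

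The last variant comes within 3% of 100, and the others are smaller. The calculation has two groups, and 100 per arm is enough for it. The sample size is not in dispute.

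**2. Number of options, side by side.**

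| Place | Number |
|---|---|
| Front matter, Randomization | 3, unnamed |
| 3.1 | 2 (either/or) |
| 3.3 | not given |
| 3.4 | 2 |
| 4.2 | 2 |
| 5.1 | 2 (control and experimental) |
| 6.1 | 2 |

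No section confirms three. The device comparison in Section 3.2.2 makes one three-option list conceivable: mucopexy alone, THD plus mucopexy, AMI plus mucopexy. That is an inference; no section says that the device is randomised.

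**3. Group B, side by side.**

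| Place | Groups compared |
|---|---|
| Title, 2, 3.1, 3.2.1 | mucopexy with DGHAL; mucopexy without DGHAL |
| 4.2 | DGHAL with mucopexy; DGHAL without mucopexy |
| 4.2.1.3 | assumes a non-Doppler group that receives mucopexy |

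In Section 4.2 both groups receive Doppler-guided ligation and differ in mucopexy. In the primary aim both receive mucopexy and differ in Doppler-guided ligation. The omitted component is reversed, and the non-Doppler group of Section 4.2.1.3 does not exist in Section 4.2.

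**4. Illustration of the allocation (assumptions, not protocol content).** Total 2 × 100 = 200. With two options at 1:1, the expected split is 100 against 100. With the three options inferred in step 2, equal weights and the two device options pooled, it is 200/3 ≈ 67 against 133. With weights 2:1:1 it is 100 against 50 + 50 = 100, which agrees with Section 5.1.

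**5. Whether primary power is at stake.** Power = 2Φ(0.15/√(0.09(1/n₁ + 1/n₂)) − z) − 1, with z = 1.645 or 1.960:

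- 100 vs 100: 0.15/0.0424 = 3.54, giving 94% or 88%.
- 67 vs 133: 0.15/0.0449 = 3.34, giving 91% or 83%.

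Both exceed the stated 80%.

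**The case against.** The strongest reply is that both are drafting slips that the rest of the protocol resolves. A single figure in the front matter stands against five sections that describe two arms. The group B wording stands against the title, the hypothesis, the design, the primary aim and the technique section that a surgeon would follow. This is fair as to likely intent and lowers the practical risk. It does not remove the need to correct, because the two discrepant texts are the allocation instruction and the arm definition. Nor can the three be dismissed with certainty, since the device comparison offers a plausible origin for it.

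A reader might also infer more than the document supports:

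- *That the list has a 1:2 ratio in conflict with 100 per arm.* The front matter states no ratio. The 67-against-133 split needs an inferred set of options and equal weights, and 2:1:1 weights would restore 100 against 100.
- *That the primary comparison loses power.* Under the pooled reading it stays above 80%. Pairwise comparison of about 67 against 67 would have roughly 79% or 65% power (5% or 2.5% per side), but the protocol states no such unpooled three-arm design.
- *That the device comparison is confounded by centre or surgeon.* This is possible, but no section says that devices vary in that way. What stands is only that, with two arms, no rule makes the comparison randomised.
- *That Sections 3.1, 3.4 and 4.2 must be rewritten if three options are meant.* Their two-group wording can be read as two pooled groups.

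**Conclusion.** Wrong as written, in two separate internal contradictions. First, the front matter assigns three unnamed options by simple randomisation, while Sections 3.1, 3.4, 4.2, 5.1 and 6.1 describe two arms. Second, Section 4.2 defines group B in a way that conflicts with the title and Sections 2, 3.1, 3.2.1 and 4.2.1.3, so that neither of its groups is literally the mucopexy-alone arm.

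Both conclusions rest on the current text alone and need no assumption. The point concerns consistency and changes no figure in the plan: the 100 per arm stands for a two-group comparison. The 67-against-133 split only illustrates how far apart two readings could be, under the assumptions given with it. The correction should be made, because it decides what the list must contain and whether the device comparison can be called randomised.

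**What to change.** Reconcile the front-matter Randomization paragraph with Sections 3.1, 3.4, 4.2, 5.1 and 6.1, then check the list set-up against the result.

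- **If two arms are meant:** change the front matter to two named options allocated 1:1 (100 per arm, 200 in total). Report the THD-versus-AMI comparison of Section 3.2.2 as non-randomised, since Section 4.2.1.2 gives no device-assignment rule.
- **If three options are meant:** name them, state the allocation ratio and the total, and say which are pooled for the primary contrast. Section 5.1 needs changing only if the groups compared are then not 100 against 100.

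Separately, reconcile the group B wording in Section 4.2 with the title and Sections 2, 3.1, 3.2.1 and 4.2.1.3.

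The cost is amendment wording and one check of the list; the central randomisation service stays. Confirming two arms adds no patients, though the device comparison then carries less weight. Three options of 100 each would need 3 × 100 = 300 patients.

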1. INTRODUCTION

1.1 Background

Hemorrhoidal disease is one of the most common proctological disease affecting the general population from the mid-teens onward with considerable implications for the National Health Service (NHS) both from an economic point of view and from surgeon's workload¹. Even if hemorrhoids are a benign condition, they severely impact patients' quality of life. In fact, symptoms include bleeding, pain, prolapse, soiling and itch. The treatment of hemorrhoidal disease is directed at relieving its related symptoms.

1.2 Management of disease

While Goligher's grade I-II hemorrhoids can be readily treated with conservative measures and grade IV hemorrhoids find the gold standard treatment in the hemorrhoidectomy, several minimally invasive treatment options, including Doppler-guided hemorrhoidal artery ligation and mucopexy have been introduced for the management of grade III hemorrhoids with the aim of minimizing postoperative pain and sparing the sensitive anoderm

1.3 Doppler guided hemorrhoidal artery ligation

Improved understanding of the pathogenesis of haemorrhoids and of the complications associated with excisional haemorrhoidectomy led to the invention of newer surgical procedures, including Doppler guided haemorrhoidal artery ligation (DGHAL).

This technique was introduced in 1995 by Morinaga et al. and consists in the use of a proctoscope with a Doppler transducer that detect the arterial structures[1].

Since DGHAL does not involve tissue excision, it is expected to be associated with reduced postoperative pain if compared with hemorrhoidectomy[2].

In the last decade several devices (THD and AMI/ HAL-RAR – Hemorrhoidal Artery Ligation and Recto Anal Repair) have been developed in order to improve and facilitate the execution of the technique, making easier the procedure [3, 4].

1.4 Mucopexy

The addition of suture mucopexy to DGHAL has extended the indication of this technique to III degree hemorrhoids with encouraging results in terms of postoperative pain and complication and long term recurrences.

About 6 mucopexy with resorbable sutures are usually performed with this procedure starting from 2 o'clock in clockwise direction.

A RCT and some case series have cast doubts on the usefulness of making DGHAL, claiming that mucopexy alone can yield similar results and with less time (Aigner et al). However, these studies have some weak points including small sample size and use of different devices.

2. STUDY HYPOTHESIS

The hypothesis of the study is that a simple mucopexy procedure by suture-fixation of anal cushion without the aim of a Doppler device, could be as effective as DGHAL and mucopexy to manage prolapsing grade III hemorrhoids.

3. STUDY DESIGN

3.1 General Design

Prospective, multi-centre, parallel-arm randomized controlled equivalence trial. Eligible patients will be randomized to either mucopexy without Doppler guided artery ligation or mucopexy with doppler guided hemorroidal artery ligation.

3.2 Endpoints

[figure not shown]
3.2.1 Primary

[figure not shown]
Primary aim of the Hamlet trial is to demonstrate that mucopexy without DGHAL for grade III haemorrhoids have equivalent recurrence rate at 1 year follow up of DGHAL with mucopexy procedure

3.2.2 Secondary

- SAFETY: Demonstration that the new treatment will not add related morbidity
- Comparison of the outcome among the two devices (THD and AMI/ HAL-RAR) for DGHAL

_

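### The secondary safety aim is to demonstrate no added morbidity, but the only test stated for it is a two-tailed chi-square test of difference, which cannot demonstrate that at any event rate

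*Protocol*

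**What the plan says.** Section 3.2.2 of the protocol lists the safety objective as "Demonstration that the new treatment will not add related morbidity". I take the new treatment to be mucopexy without Doppler guidance, following sections 2 and 3.1.

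Section 3.6.1 defines four adverse events: urinary retention, pyrexia, surgical site infection and postoperative bleeding. Each is defined so that a patient either has it or does not. No expected rate is given for any of them.

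Section 5.2 names the "Chi-square test for categorical variables" and adds "All hypotheses will two-tails with p < 0.05 considered as statistically significant". Nothing in that section sets safety apart from other outcomes.

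Section 5.1 sizes the trial for the primary aim only. It says that "100 subjects per arm will suffice for accepting of the equivalent hypothesis with power of 0.8 and a type I error probability of 0.05", with "an equivalent limit of 15% and expected percentage of success in both control and experimental group of 90" percent. That limit belongs to the success rate behind the recurrence endpoint and is not attached to morbidity.

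**The concern.** The aim and the method answer different questions. To demonstrate that a treatment adds no morbidity is to rule out an increase larger than some stated amount, so the evidence has to be an upper bound on the difference. A two-tailed chi-square test takes equality as its null hypothesis. It can reject equality, but failing to reject says only that the data did not show a difference. The smaller the trial, or the rarer the event, the easier it is to get that result.

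The protocol states both the aim and the test, and they do not fit. That is a fault in what the document says, and does not depend on detail that an analysis plan might add.

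The trial's case for dropping the Doppler step is that mucopexy alone may work as well (section 2) and cost less (section 3.2.3). A statement that it adds no morbidity would support adoption, and it should not rest on a p-value above 0.05.

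**Working it through.** **Inputs from the protocol.** 100 patients per arm (5.1); two arms (4.2, "They will be randomized in 2 groups"); chi-square test, two-tailed, 0.05 (5.2).

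**Inputs that are assumptions.** All morbidity rates, all morbidity margins, and no dropout.

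**Step 1: the protocol's own sample size.** This is for the primary aim: 90% success in both arms, limit 15 points, power 0.8. For two one-sided tests, n per arm = 2p(1-p)(z₁₋ₐ + z₁₋ᵦ/₂)² / m².
- At 0.05 per side: 0.18 × (1.645 + 1.282)² / 0.0225 = 68.5, so 69.
- At 0.025 per side: 0.18 × (1.960 + 1.282)² / 0.0225 = 84.1, so 85; with a continuity correction, 97.

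The stated 100 is therefore enough for the primary aim: power at 100 per arm is 0.94 or 0.88 respectively. It is not in dispute here, but it says nothing about morbidity.

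**Step 2: can the stated test meet the safety aim?** Its null hypothesis is equal rates. The aim needs rejection of a null hypothesis that morbidity is higher by some margin or more. No margin is given and the test does not use one. This holds at any event rate and any sample size.

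**Step 3: how often a real doubling would be non-significant.** The normal approximation to the power is Φ{(|p₂ - p₁|√n - 1.96√[2p̄(1-p̄)]) / √[p₁(1-p₁) + p₂(1-p₂)]}. For 5% vs 10%, p̄ = 0.075 and √n = 10:

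(0.5 - 1.96 × 0.3725) / 0.3708 = -0.62, so power is 26.7%.

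Exact binomial enumeration of the uncorrected Pearson test gives:

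| Assumed rates | Power at 100 per arm | Doubling missed |
|---|---|---|
| 3% vs 6% | 15% | 85% |
| 5% vs 10% | 27% | 73% |
| 10% vs 20% | 52% | 48% |
| 15% vs 30% | 73% | 27% |

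The uncorrected test is the favourable case. For 5% vs 10%, power is 17% with the Yates correction and 19% with Fisher's exact test.

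**Step 4: what a non-significant result can hide.** Take 5/100 vs 12/100. The pooled rate is 17/200 = 0.085. The standard error is √(2 × 0.085 × 0.915 / 100) = 0.0394, so z = 0.07 / 0.0394 = 1.77 and p = 0.076. The Wilson limits are 2.2% to 11.2% and 7.0% to 19.8%. The Newcombe interval for the difference is then:
- lower: 0.07 - √[(0.120 - 0.070)² + (0.1118 - 0.050)²] = -0.009
- upper: 0.07 + √[(0.1981 - 0.120)² + (0.050 - 0.0215)²] = +0.153

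The result is not significant, yet increases of up to about 15 points are not excluded. With 5 vs 5 events the Newcombe interval is ±6.8 points.

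**Step 5: if the aim keeps its demonstrative form.** With equal true rates p and margin m, one-sided 0.025, power is Φ(m / √[2p(1-p)/100] - 1.96).

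| True morbidity in both arms | 5-point margin | 10-point margin | 15-point margin |
|---|---|---|---|
| 5% | 37% | 90% | over 99% |
| 10% | 22% | 65% | 94% |

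Whether 100 per arm suffices depends on a margin that the protocol does not state.

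**The case against.** The strongest objection is that the harm is inferred. A reader might conclude that the protocol commits the trial to reporting p > 0.05 as proof of safety. It does not say so. Section 5.2 only defines what counts as significant, and it also has results expressed as frequencies, so event rates by arm would be visible. This stands as a limit on the point. What remains is that the protocol promises a demonstration and names no criterion by which it could be made other than that test.

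A second objection is that margins and interval rules for a secondary endpoint are commonly left to an analysis plan, which is not at hand. This also stands, so a missing margin is no fault in itself. The mismatch between the stated aim and the stated test is another matter, because section 5.2 covers all hypotheses.

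Two stronger readings are tempting and should be resisted:
- **That non-significance is the most likely result even if morbidity doubles.** This is true for the lower assumed baselines only. At 10% vs 20% the test is slightly more likely than not to be significant, and at 15% vs 30% clearly so. The protocol gives no rates, and its four events include urinary retention and treated pyrexia, so low rates cannot be presumed.
- **That the design cannot support any safety statement.** Step 5 shows otherwise: with 5% true morbidity and a 10-point margin, 100 per arm has about 90% power. The fault is in the stated test and the wording of the aim.

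Finally, the cause overlaps with the primary analysis, since section 5.2 lists only difference tests for aims that claim no difference. One general sentence there could serve both aims, but the 15-point limit in section 5.1 would not supply a margin for morbidity.

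**Conclusion.** The point holds as a mismatch between a stated aim and a stated method. A non-significant two-tailed chi-square test cannot demonstrate absence of added morbidity at any event rate, and the protocol offers nothing else for the purpose. That conclusion rests on the text alone.

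The size rests on assumed rates. Across the doublings tabulated, the miss rate runs from 85% down to 27%; a doubling would often be missed if baseline morbidity is below about 10%. These figures assume 100 evaluable patients per arm and the uncorrected chi-square test; dropout or a corrected test would lower the power.

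This concerns a secondary aim and leaves the primary sample size untouched. It should be corrected, but it does not threaten the trial's main question.

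**What to change.** In section 5.2, state three things:
- The between-arm risk difference for each adverse event defined in section 3.6.1 is reported with a 95% confidence interval (Newcombe or similar). Reporting event by event avoids a composite that the protocol does not define.
- A non-significant test is not read as showing that morbidity is not increased.
- The safety conclusion is worded by the largest increase that the upper limit excludes.

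In section 3.2.2, reword the aim as *to estimate the difference in morbidity between arms*. If the sponsor prefers to keep a demonstration, state a morbidity margin, justify it, and add a matching confidence-interval rule, having checked the power at 100 per arm for that margin.

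The cost is a few sentences and one interval per adverse event, with no added patients or data. The downside is a less favourable safety statement: with 5 events in each arm, for example, the trial could say only that an increase above about 7 points is excluded.
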